Post Testing and 6-month BPG Dynamic Assessment Follow-up. Within 2-4 weeks after completing BPG training and dynamic assessment, the full sample of children and their caregivers will return to the clinic for a full gold standard neuropsychological evaluation as the caregiver once again completes the CBCL. The final step in Phase I of our study process will be when the field research assistant returns with the child one final time after 6 months to administer 1 session of the BPG games to the full sample (corresponding to an internal performance evaluation for one final time). Within 2-4 weeks of this final BPG assessment, all children and their caregivers will return to the clinic for a gold standard neuropsychological evaluation. Our rationale for choosing when to have the final assessment is based on past work: after 6 months without training, the benefits of training may begin to diminish in terms of a slower rate of change in comparison to the rate of change during the training period. This BPG performance change from post training to 6-mo follow-up will provide an additional dynamic outcome for validity analyses.

In Phase 2 of the study we will assess the static and dynamic properties of an executive behavior-focused cognitive rehabilitation game package called Village Builder. In this Phase, children allocated to the wait-list condition will complete 12 sessions of training with Village Builder in a mobile device and facilitated by a research assistant. Within 2-4 weeks of the final Village Builder session, children will attend the clinic for a gold standard neuropsychological evaluation using the same battery of tests as in Phase 1. The last visit of Phase 2 will be 6 months (+/- 4 weeks) after completion of the training, where a final session of Village Builder will be administered (static evaluation) along with the battery of neuropsychological tests. Caregivers will also complete the CBCL, SES and HOME assessments in the same study visits as their children.

Figure 6. Study visits and assessments (numbers for 1 site shown)

PHASE I

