5.2 Study goals, aims and objectives

5.2.1 Study Goal

The overall goal of this research is to adapt and validate BPG as a measure to assess cognitive changes as a child plays with BPG once (static assessment) and over the course of 12 training sessions (dynamic assessments of cognitive change over time).

5.2.2 Aims and objectives:

Aim 1: To adapt and evaluate concurrent and predictive validity of BPG static (baseline) and dynamic (during 12 training sessions) cognitive assessments at the Malawi and Uganda sites.

Objective 1.1 To evaluate whether BPG static (baseline) assessment corresponds to the gold standard static measures previously adapted to HEU, HUU, and HIV+ study cohorts at Uganda and Malawi country sites (KABC-II, TOVA, CogState).

Aim 2: To compare the validity of BPG static and dynamic assessments.

Objective 2.1 To evaluate the correspondence of BGP-based static and dynamic assessments the cohorts' prior early childhood longitudinal trajectories (KABC-II), considering the effect of proximal (e.g. HIV status) & distal (height, weight, HIV disease factors, demographic) risk factors causing developmental delay and cognitive problems.

Aim 3: To test the sensitivity of dynamic assessment to learning loss over time by evaluating how much BPG performance gains diminish during a 6-month absence of training

Objective 3.1 To assess change over time in KABC-II, TOVA and CogState scores (learning loss) 6 months after the children complete 12 sessions of BPG training, overall and by cohort.

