7.1.2 Statistical Approach by Specific Aim

Statistical analysis for Aims 1& 2. So as not to have to rely on American norms for standardizing our gold standard measures, we will use a statistical technique for standardization described from our cerebral malaria longitudinal studies with these tests.⁶⁵ [name] will evaluate the concurrent validity by computing correlation coefficients of the BPG and “gold standard” measures at intake (see Table 3) at 1 and 7 months. Correlations will be classified as: very strong ($r \geq 0.8$), strong (r range 0.6-0.79), moderate (r range, 0.4-0.59), weak (r range, 0.20-0.39), and very weak (range: 0-0.19). We will summarize the sensitivity of the BPG-based vs gold standard measures to the proximal (HIV infection) and distal factors (SES, home environment, growth) using: 1) relative validity coefficient; 2) standardized effect size;⁶⁶⁻⁶⁹ 3) standardized response mean (SRM) and Guyatt’s SRM.^{66,67,69,70} Larger values of these summary statistics correspond to greater sensitivity or ability to discriminate known groups. Interpretations similar to Cohen’s effect sizes⁶⁸ will be considered (e.g. SRM: ≥ 1.0 : excellent; 0.80-0.99: good; 0.50-0.79: moderate; and < 0.5 : weak). We will evaluate the predictive validity of the BPG-derived measures in the LME model with the repeated gold standard measures at 1 and 7 months (6-month follow-up). Covariates will include the BPG static measure at intake (baseline) and 1 month (post-training BPG; time-varying covariate), time (1 and 7 months), other covariates (proximal and distal factors, Figure 1), and number of prior neuropsychological testing sessions.

Statistical analysis for Aim 3. Two sets of the LME models will be fit: one with 3 repeated “gold standard” measures, and one with 3 BPG-derived measures. To model potential non-linear patterns over time, we will enter time as a class variable with levels of intake, 1, and 7 months. Based on past experience, we expect gains in outcomes between intake and 1 month due to training, and a slower rate of change in the subsequent 6-month period with no training. Summary statistics for change over time for the gold standard vs BPG-derived measures will be compared as described under statistical analysis for Aim 1.

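### Aim 3 compares learning loss on BPG and the gold standard only through group-level change indices; an analysis linking the 1-to-7-month changes within the same child should be added

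*Combined protocol and SAP*

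**What the plan says.** Section 5.2.2 gives Aim 3 as "To test the sensitivity of dynamic assessment to learning loss over time by evaluating how much BPG performance gains diminish" over six months without training. Objective 3.1 asks for change in KABC-II, TOVA and CogState, overall and by cohort. Section 3.0 adds the hypothesis that BPG learning loss will be especially sensitive to brain/behavior integrity in pediatric HIV.

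The analysis is in section 7.1.2: "Two sets of the LME models will be fit: one with 3 repeated “gold standard” measures, and one with 3 BPG-derived measures". Time is a class variable (intake, 1 and 7 months). Then: "Summary statistics for change over time for the gold standard vs BPG-derived measures will be compared as described under statistical analysis for Aim 1". The Aim 1 text supplies the relative validity coefficient, the standardized effect size, and "standardized response mean (SRM) and Guyatt’s SRM". It reads them this way: "Larger values of these summary statistics correspond to greater sensitivity or ability to discriminate known groups".

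Two other analyses in 7.1.2 do link the instruments child by child. One computes "correlation coefficients of the BPG and “gold standard” measures at intake (see Table 3) at 1 and 7 months". The other assesses "predictive validity of the BPG-derived measures in the LME model with the repeated gold standard measures at 1 and 7 months", with BPG at intake and at 1 month as the listed BPG covariates.

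Section 5.1 says of the loss period: "This BPG performance change from post training to 6-mo follow-up will provide an additional dynamic outcome for validity analyses".

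**The concern.** Each index is computed on one instrument at a time. SRMs use the mean change and an SD; effect size and relative validity use contrasts between known groups. None uses the pairing of a child's BPG change with the same child's gold-standard change, so two similar mean curves could come from different children.

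The instruments are also not on an equal footing. Half the sample practises BPG for 12 sessions, while KABC-II, TOVA and CogState are only retested. A larger gain and fall-back on BPG is what practice and forgetting of the games would produce, whatever happens to cognition. If larger is read as more sensitive, that difference could be reported as superior sensitivity to cognitive loss.

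Section 5.1 suggests that the investigators meant to validate the BPG loss score, but the analysis section does not carry this through.

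**Working it through.** **Plan's own figures.** Section 7.1.2 sizes Aims 1 to 3 on known-groups differences. For d = 0.26, n per group = 2(1.96 + 0.8416)²/0.26² = 232.2, rounded up to 233; at 240 the power is Φ(0.26·√120 − 1.96) = 0.813. For 120 HIV+ against 240 at d = 0.31, power is Φ(0.31·√80 − 1.96) = 0.792. Both agree closely with the plan. Neither concerns change or agreement of changes, and the documents give no figure for Aim 3 itself.

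**Inputs for the check.** Trained children: 50% of 600 = 300 (section 5.1). Alpha 0.05, two-sided (7.1.2). The SRMs, stabilities and correlations below are assumptions, because the documents state none.

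**Step 1: SRM and the child-level link.** SRM = mean(change)/SD(change), computed per instrument. In simulation with n = 300 and true SRMs of −0.5 (BPG) and −0.3 (gold standard), the average estimates were:

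| Change-change correlation | BPG SRM | Gold-standard SRM |
|---|---|---|
| 0 | −0.50 | −0.30 |
| 0.3 | −0.51 | −0.30 |
| 0.6 | −0.50 | −0.30 |

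The expected SRMs do not move with the correlation, whatever sizes are assumed.

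**Step 2: how often BPG shows the larger SRM (absolute sizes, n = 300).**

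| Gold vs BPG SRM | Correlation 0 | Correlation 0.5 |
|---|---|---|
| 0.2 vs 0.3 | 88–89% | 95–96% |
| 0.3 vs 0.5 | 99% | 99.9% |
| 0.2 vs 0.5; 0.3 vs 0.8 | 100% | 100% |

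First row in closed form: at correlation 0 the variance of the SRM difference is about 2/300 + (0.2² + 0.3²)/600 = 0.00688, SD 0.083, and Φ(0.1/0.083) = 0.886. Correlation does narrow the sampling spread of the difference, hence the shift to 95–96%, but BPG is favoured either way. At correlation 0 both mean changes are significant in 93–100% of runs; for example, Φ(0.2·√300 − 1.96) = 0.93 for the smallest.

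**Step 3: do the level correlations fill the gap?** With unit variances, common within-visit correlation r, stability s and cross-lagged correlation c, the change-change correlation is (2r − 2c)/(2 − 2s). With r = c it is zero. A simulated case had r = 0.50 at both 1 and 7 months (moderate on the plan's scale), SRMs of −0.50 and −0.30, and a change-change correlation of 0.00. With r of 0.3 or 0.5 and s from 0.6 to 0.8, any value from −1 to 1 is possible. With r = 0.7 and s = 0.6 the range narrows only to −0.5 to 1.

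**Step 4: does the predictive model fill it?** Its listed BPG covariates stop at 1 month, so BPG change from 1 to 7 months does not enter.

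**Step 5: precision of a change-change correlation (Fisher z).**
- n = 300: detectable r at 80% power = tanh(2.8016/√297) = 0.161. Power for r = 0.2 is Φ(0.2027·√297 − 1.96) = 0.94. An observed 0.30 has a 95% CI of 0.19 to 0.40.
- n = 285 (5% loss, from the retention above 95% cited in 5.6.7): detectable r = 0.165.
- By cohort, section 5.6.1 (per-site numbers, two sites) gives 120 trained HEU, 120 HUU and 60 HIV+. Detectable r is tanh(2.8016/√117) = 0.25 and tanh(2.8016/√57) = 0.36.

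**Step 6: is an adjusted regression a substitute?** Regressing the 7-month gold-standard score on 1-to-7-month BPG change, given both 1-month scores, in effect tests the 7-month BPG level. Take r = 0.5, s = 0.7, c = 0.5. The change-change correlation is 0. The partial covariance is 0.5 − 0.44 = 0.06 and each residual variance is 1 − 0.52 = 0.48, so the partial r = 0.06/0.48 = 0.125. This rejects with probability Φ(0.1257·√295 − 1.96) = 0.58 at n = 300. The two analyses can disagree.

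**The case against.** The strongest reply is that the plan answers the question it set. Aim 3 asks how far BPG gains diminish, Objective 3.1 asks for gold-standard change by cohort, and the hypothesis about pediatric HIV is largely a known-groups question. Two mixed models address these. The borrowed indices include relative validity and effect sizes, and practice and forgetting that were uniform across cohorts would not discriminate on those. This stands, and it is why the planned analyses should stay. It does not supply evidence that loss on one instrument goes with loss on the other in the same child.

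A reader might infer that the study never links BPG to cognition in individual children. The documents do not support that: the primary outcome in section 5.3 and the predictive model are such links, and a BPG score wholly unrelated to cognition should show up there. The gap is confined to change from 1 to 7 months.

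A further objection is that the study's thesis is that dynamic BPG captures what static tests miss. If the gold standard responds weakly to loss, the association will be small even for a good tool. This also stands, and it rules out using the association as the only criterion.

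**Conclusion.** The concern holds as a gap in Aim 3. The SRM comparison cannot show whether BPG loss tracks cognitive loss within children, training can enlarge the BPG SRM by itself, and the validity use of BPG loss announced in section 5.1 has no analysis in 7.1.2. Under the assumed SRMs, BPG would look more sensitive in 88% to 100% of studies with no child-level link. Those percentages depend on assumed sizes; that the expected SRM ignores the link does not.

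It would be too strong to say that an invalid BPG would pass Aim 3. The plan sets no pass rule; it compares statistics under a larger-is-more-sensitive reading. The calculations also show only what the indices cannot distinguish. They do not show that BPG change is unrelated to cognition in these children.

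**What to change.** Keep the planned mixed models, SRMs and known-groups indices. Add to the Aim 3 text of section 7.1.2:

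- In BPG-trained children, fit one bivariate mixed model to BPG and gold-standard scores at intake, 1 and 7 months, and report the child-level correlation of the 1-to-7-month changes with a 95% CI.
- Name the gold-standard score in advance (for example KABC-II MPI, one of seven KABC-II primary variables in section 5.6.3), and name the BPG score too.
- State that a larger BPG SRM alone will not be read as greater sensitivity to cognitive loss, and report it with this association.
- Do not make the association the sole gate for Aim 3, and do not offer the adjusted regression as equivalent.
- If results by cohort are shown, treat them as descriptive, given 60 trained HIV+ children.

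The cost is SAP wording and one model on scores already scheduled, with no extra children for the overall analysis. The downside is that change scores are noisy. If both changes had reliability 0.5 (an assumption), an observed 0.16 would correspond to a true correlation of about 0.16/0.5 = 0.32. A small estimate should therefore be reported as inconclusive about BPG, since an insensitive gold standard could also produce it.

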5.0 NEURODEVELOPMENTAL ASSESSMENT PROTOCOL DESIGN

5.1 Overview of Study Design:

[figure not shown]
Static and Dynamic Assessment Process for Each Study Child. Figure 6 provides an overview of study visits and assessments. Following enrollment and physical and medical exams, each child will return to the clinic with their principal caregiver for a half-day of gold standard neuropsychological assessments (KABC-II, TOVA, CogState). At this time the caregiver will complete the Achenbach CBCL questionnaire for school-age children, the Caldwell HOME scale, the SES material possessions evaluation, and the Hopkins Symptom Checklist-25 (caregiver psychological well-being). We will explain assessments and provide instructions in the local language. Study assessments will proceed in two phases. In Phase I, children will be randomized to start BPG trainings (50% of sample) or to a wait-list condition. Within a week after baseline assessment, the full sample of children will be contacted by a field research assistant and facilitate a first BPG session. This first session will be completed by the full sample because it will be considered as an internal performance evaluation session with BPG and will be completed on a tablet, supervised by the field research assistant. This will be done as part of the 50-60 minutes training session on the 5 BPG games (about 10 minutes per game), and will constitute the BPG static assessment. Thereafter, the field research assistant will return with children allocated to the BPG trainings (50% of sample) at a convenient time and supervise BPG training several times per week until 12 training sessions are completed. The 12th session internal evaluation performance measures for the 5 core games and one added EF game will provide the endpoint for BPG dynamic assessment (gain in BPG performance from session 1 to session 12). Because BPG training will occur on a tablet connected to the internet through the mobile network, performance data can be uploaded for analysis via the MSU GEL lab principal server, as done in the Kayunga Uganda CCRT study with BPG ¹.

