Sample sizes for Aims 1, 2, and 3. Sample size considerations are based on having sufficient power to discriminate known groups based on the proximal factor of HIV status/exposure, a key factor for Aim 1. The preliminary data from PROMISE ND study indicate that the differences in the composite neurodevelopmental score (the Mullen Scale of Early Learning) between HEU and HUU cohorts corresponded to the effect size of Cohen's $d=0.26$ (difference between the means of 0.26 of the standard deviation). To detect this difference between HUU and HEU cohorts, $n=240$ per cohort is needed for power ≥ 0.80 in two-tailed tests at 0.05 level of significance. Based on the preliminary data, the effect size d for comparisons of the HIV vs HUU or HEU is at least 0.31. This can be detected with power ≥ 0.80 with $n=120$ in the HIV group. Therefore, the proposed total sample size for both sites combined is $n=240$ HUU; $n=240$ HEU; and $n=120$ for HIV+ children.

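### The 0.80 power stated for all three aims rests on 240/240/120 children, but the trained BPG gain will exist in only 120/120/60

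*Combined protocol and SAP*

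**What the plan says.** Section 7.1.2 covers the three aims with one paragraph: "Sample sizes for Aims 1, 2, and 3. Sample size considerations are based on having sufficient power to discriminate known groups". For HEU vs HUU it takes d = 0.26 from a Mullen composite score in the earlier cohort study and says that 240 "per cohort is needed for power ≥ 0.80 in two-tailed tests at 0.05 level of significance". For the HIV+ group it says "the effect size d for comparisons of the HIV vs HUU or HEU is at least 0.31" and that 120 children suffice. The total is 240 HUU, 240 HEU and 120 HIV+.

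Section 5.1 defines the dynamic measure. The session-12 performance measures "will provide the endpoint for BPG dynamic assessment (gain in BPG performance from session 1 to session 12"). After the first session, which all children complete, "the field research assistant will return with children allocated to the BPG trainings (50% of sample") until 12 sessions are done. A second dynamic outcome follows: "This BPG performance change from post training to 6-mo follow-up will provide an additional dynamic outcome for validity analyses".

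Section 5.6.1 assigns 60 of 120 HEU, 60 of 120 HUU and 30 of 60 HIV+ children to BPG training. Section 5.6.6 (Tables 2 and 3) agrees: training visits are for half the sample, and the wait-list group has one BPG session at post-test and one at 6 months. In Phase 2, "children allocated to the wait-list condition will complete 12 sessions of training with Village Builder".

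Section 7.1.2 gives no n, detectable difference or precision for the trained half, and its listed model covariates do not name training arm.

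**The concern.** A sample-size statement headed with all three aims should hold for the measures on which those aims depend. Aim 2 compares BPG static with BPG dynamic assessment. Aim 3 asks how far training gains fade. The central hypothesis in Section 2.0 is partly that gains capture HIV effects across cohorts better than static scores do. All three need the trained gain, which half the children will not have.

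At stake is a reader's trust in the static-versus-dynamic result. A team that takes the 0.80 at face value would expect cohort differences in gain to be estimated as precisely as cohort differences in intake scores. They will not be. The plan also does not fix which children each estimate uses, so a static estimate from 600 children could be set beside a dynamic estimate from 300.

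**Working it through.** **Inputs.** From Section 7.1.2: two-sided alpha 0.05, power 0.80, d = 0.26 and 0.31, and full cohorts of 240/240/120. The trained numbers come from Section 5.6.1. Its lists run 001–120 for HEU and HUU and 01–60 for HIV+, which match the per-site targets in Sections 5.4 and 5.6. They are therefore per-site counts: 60/60/30 trained per site, times two sites = 120/120/60, or 300 children.

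**The plan's own figure.** For two means on the d scale, d = 0.26 needs 233 per cohort, and 240 vs 240 gives power 0.811 (noncentral t). For d = 0.31 with 120 vs 240, power is 0.790; the detectable d there is 0.314. The stated sizes reproduce, the HIV+ one marginally.

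**Detectable d at 0.80 power.** d = (1.960 + 0.842) × √(1/n₁ + 1/n₂).

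- 120 vs 120: 2.802 × √(1/120 + 1/120) = 0.362 (t-based 0.363).
- 60 vs 120: 2.802 × √(1/60 + 1/120) = 0.443 (t-based 0.445).

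**95% half-width for d.** 1.96 × √[(n₁+n₂)/(n₁n₂) + d²/(2(n₁+n₂))].

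- HEU vs HUU, d = 0.26: full 1.96 × √(0.00833 + 0.00007) = 0.180; trained half 1.96 × √(0.01667 + 0.00014) = 0.254.
- HIV+ vs either, d = 0.31: full 1.96 × √(0.01250 + 0.00013) = 0.220; trained half 1.96 × √(0.02500 + 0.00027) = 0.312.

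| Comparison | Children | Detectable d | 95% half-width |
|---|---|---|---|
| HEU vs HUU | 240 vs 240 | 0.26 | 0.18 |
| HEU vs HUU, trained | 120 vs 120 | 0.36 | 0.25 |
| HIV+ vs either | 120 vs 240 | 0.31 | 0.22 |
| HIV+ vs either, trained | 60 vs 120 | 0.45 | 0.31 |

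Section 7 makes no allowance for loss. If 5% of the trained children are lost (an assumption, from the retention above 95% cited in Section 5.6.7), 114 vs 114 and 57 vs 114 give detectable d of 0.37 and 0.46.

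**Same children or mixed samples for static minus dynamic d.** Let v be the variance of d in the trained half, vf that in the full sample (leading term only), and ρ the assumed correlation of the two measures. The half-width is 1.96√(2v(1−ρ)) with the same children, and 1.96√(vf + v − 2ρ·vf) with static in all and dynamic in half. HEU vs HUU has v = 240/120² and vf = 480/240². HIV+ has v = 180/(60×120) and vf = 360/(120×240).

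| ρ | HEU vs HUU: same / mixed | HIV+: same / mixed |
|---|---|---|
| 0.3 | 0.30 / 0.28 | 0.37 / 0.34 |
| 0.5 | 0.25 / 0.25 | 0.31 / 0.31 |
| 0.7 | 0.20 / 0.23 | 0.24 / 0.28 |

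**The case against.** The plan's arithmetic is sound for what it computes, and its text calls HIV status a key factor for Aim 1. That is fair: the fault lies in the scope of the statement, not in the sum. But the heading claims all three aims, and Aim 1 in Section 5.2.2 itself includes dynamic assessment.

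The benchmark is borrowed. The 0.26 is a Mullen difference, no d for BPG gain appears anywhere, and the plan expects dynamic measures to be more sensitive. This stands. A reader might infer that the cohort comparison of gains is bound to be underpowered. The documents do not support that, because they give no effect size for the gain and Section 7.1.2 names no significance test of it.

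The primary outcome in Section 5.3 is a set of correlations, and half the central hypothesis concerns added variation in gold-standard scores. Table 1 in Section 4.1 reports that dynamic measures from a different game package added to the baseline score with 104 children; here 300 will be trained. This also stands: the calculation above does not assess those analyses.

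Wait-list children have BPG scores at intake, post-test and 6 months, so change can be computed for them. True, but it is change without training, not the gain that Section 5.1 defines.

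Pooling HEU and HUU would help the HIV+ comparison, yet 60 vs 240 still gives a detectable d of about 0.41, above 0.31. The plan quantifies no gain from covariates.

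Two further inferences are tempting. One is that relative validity would penalise the dynamic measure because of its smaller n. The plan does not define that coefficient, nor does it say that 300 will be set against 600. The other is that leaving out training arm costs material power. The documents give no size for the training shift, and allocation is even within each cohort.

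**Conclusion.** The concern holds as a matter of scope. The stated power of at least 0.80 is not delivered for the trained BPG gain and post-training loss at the planned effect sizes. In 120/120/60 children the detectable d is about 0.36 and 0.45, against planned values of 0.26 and at least 0.31, and the intervals are about 1.4 times as wide (0.254/0.180 and 0.312/0.220). Adequacy for the gain is not shown; it is not disproved.

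This rests on the per-site reading of Section 5.6.1 and on unadjusted two-group comparisons with no loss. It leaves the full-sample intake comparisons intact.

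A related gap is that the 1- and 7-month models pool trained and untrained children without naming arm. Section 4.1 expects more severely affected children to benefit less from training, so cohort differences may themselves differ by arm. It should be fixed before analysis.

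**What to change.** In Section 7.1.2:

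1. Limit the 0.80 statement to cohort comparisons of full-sample measures at intake, noting about 0.79 for HIV+ at exactly d = 0.31.
2. For the trained BPG gain and loss, state n = 120/120/60, detectable d of about 0.36 and 0.45, and 95% half-widths of about 0.25 and 0.31.
3. Add randomised training arm to the models that pool arms at 1 and 7 months, with arm-by-time where intake is one of the repeated measures. Examine arm-by-cohort.
4. Compare BPG static with BPG dynamic sensitivity in the same 300 trained children, with confidence intervals. Report the full-sample static estimate separately.

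Before stating an n for the executive-function dynamic measure, reconcile two parts of Section 5.1. One puts an added executive-function game in the trained half's session-12 endpoint. The other says of Phase 2 that "we will assess the static and dynamic properties of an executive behavior-focused cognitive rehabilitation game package called Village Builder", with that training given to the wait-list half. Also align Sections 3.0 and 5.4, which read as if every child trains on BPG.

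The cost is wording and model terms, with no added children or visits. The stated figures for the dynamic measure become less favourable. Item 4 gives slightly wider intervals if the two measures correlate below about 0.5, and narrower ones above that.

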With NIH funding we previously developed BPG (Brain Powered Games), a CCRT (Computerized Cognitive Rehabilitation Therapy) digital games package for HIV+ school children in the sub-Saharan. As a child plays, BPG gathers game data that can be used for neurocognitive assessment. In this new study, we will further evaluate the capability of BPG as a test for neurodevelopment. In a second phase, we will add an award-winning game developed at the MSU-GEL lab that will train executive function (EF), allowing us to dynamically assess this often-neglected neurocognitive domain in previously tested and well-characterized HIV+, HEU and HUU cohorts of children.

In Study Aim 1 we will adapt and evaluate concurrent and predictive validity of BPG. Here we will evaluate whether BPG as a static (baseline) assessment corresponds to a gold standard of static measures (KABC-II,

TOVA, CogState). Compared to these, we hypothesize that dynamic BPG assessments will be feasible and acceptable, providing for a more sensitive evaluation of brain/behavior function as affected by more proximal factors of HIV exposure, disease and treatment. We also hypothesize that dynamic assessments will be more sensitive to distal developmental risk factors (e.g., SES, nutrition/growth, maternal caregiving quality), measured in early childhood in study cohorts.

In Study Aim 2, we will compare the validity of BPG static and dynamic assessments. Here we will validate BPG static and dynamic assessments with a gold standard of neuropsychological tests previously used with school-age children at our two study sites (Kampala, Uganda and Blantyre, Malawi). Cohorts will be well characterized due to participating in our previous NIH-sponsored HIV clinical trials. We hypothesize that BGP-based static and dynamic assessments will be sensitive to cohorts' prior longitudinal trajectories as affected by proximal and distal risk factors that cause developmental delay and cognitive problems, as measured in our previous clinical trial studies with these cohorts. The executive function game will prove especially sensitive.

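### The stated power of at least 0.80 covers a cohort difference on one score held by all children; it does not extend to between-measure comparisons of sensitivity, or to the BPG dynamic score

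*Combined protocol and SAP*

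**What the plan says.** The last paragraph of Section 7.1.2 is headed "Sample sizes for Aims 1, 2, and 3". It gives its basis as "Sample size considerations are based on having sufficient power to discriminate known groups based on the proximal factor of HIV status/exposure, a key factor for" the first aim. Two contrasts follow. For HEU vs HUU the planning effect is Cohen's d=0.26 on the Mullen composite from PROMISE ND, a "difference between the means of 0.26 of the standard deviation", for which n=240 "per cohort is needed for power ≥ 0.80 in two-tailed tests at 0.05 level of significance". For the infected cohort, "the effect size d for comparisons of the HIV vs HUU or HEU is at least 0.31", and 120 HIV+ children are said to give the same power.

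For Aims 1 and 2 the same section says: "We will summarize the sensitivity of the BPG-based vs gold standard measures to the proximal (HIV infection) and distal factors". The tools are the relative validity coefficient, the standardized effect size and standardized response means (SRM). Larger values are read as greater sensitivity. No test, confidence interval or decision rule is attached to a comparison between measures.

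Section 3.0 hypothesizes that dynamic BPG assessment improves on the gold standards, "providing for a more sensitive evaluation of brain/behavior function as affected by more proximal factors of HIV exposure, disease and treatment". Section 5.2.2 has "Aim 2: To compare the validity of BPG static and dynamic assessments".

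Section 5.1 trains 50% of the sample with BPG in Phase I and defines the dynamic endpoint as the gain from session 1 to session 12. Section 5.6.1 sends 60 of 120 HEU, 60 of 120 HUU and 30 of 60 HIV+ children to training. These are the per-site targets, so over two sites the trained children number 120, 120 and 60. Wait-list children have single BPG sessions and later train with Village Builder, a different game.

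**The concern.** A cohort difference on one score asks whether d differs from zero. A claim that BPG is more sensitive than KABC-II, or dynamic BPG more sensitive than static, asks whether one d exceeds another in the same children. The target is then only the excess over the comparator, and the standard error depends on the correlation rho between the two measures. Section 7.1.2 gives neither an expected excess nor a rho, although its heading covers all three aims.

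The dynamic score adds a separate problem. The quoted cohort sizes are for the full sample, and half of those children have no session 1-to-12 gain.

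At stake is how the results are read. If measures are ranked on point estimates without intervals, a ranking produced by sampling error can be reported as superior sensitivity, or a real advantage can be dismissed. The power heading would lend either reading support that it has not earned.

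**Working it through.** **1. The plan's own figures.** Inputs from Section 7.1.2: d=0.26 with 240 vs 240; d=0.31 with 120 vs 240; two-sided 0.05. Power = Φ(d/√(1/n1+1/n2) − 1.96).
- 240 vs 240: 0.26/0.0913 = 2.848, power 0.813 (noncentral t: 0.811).
- 120 vs 240: 0.31/0.1118 = 2.773, power 0.792 (noncentral t: 0.790).

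The plan does not name a test, but a two-sample comparison of means reproduces it, to rounding in the second case.

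**2. Same contrasts on the dynamic score (trained half).**
- 120 vs 120: 0.26/0.1291 = 2.014, power 0.52.
- 60 vs 120: 0.31/0.1581 = 1.961, power 0.50.

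**3. Detectable difference between two measures in the same children.** For scores standardized within the sample, the approximate standard error of dA − dB is √(2(1−rho)(1/n1+1/n2)). The difference detectable with 80% power is 2.80 times that. The plan gives no rho for BPG, so a range is assumed. The only guide is Table 1 in Section 4.1, where dynamic measures from a different package (Captain's Log) correlate 0.24 to 0.47 with the KABC-II MPI.

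| rho | HEU vs HUU, 240/240 | HEU vs HUU, 120/120 | HIV+ vs other, 120/240 | HIV+ vs other, 60/120 |
|---|---|---|---|---|
| 0.3 | 0.30 | 0.43 | 0.37 | 0.52 |
| 0.5 | 0.26 | 0.36 | 0.31 | 0.44 |
| 0.7 | 0.20 | 0.28 | 0.24 | 0.34 |
| 0.8 | 0.16 | 0.23 | 0.20 | 0.28 |

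The 240/240 and 120/240 columns suit static BPG vs gold standard. The 120/120 and 60/120 columns suit any contrast that uses the dynamic score. For dynamic vs static BPG, rho could be near zero, because the gain is measured from the same session-1 score that serves as the static measure. At rho 0 and 120/120: 2.80 × √(2 × 2/120) = 2.80 × 0.1826 = 0.51.

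**4. Illustrative power.** Assume the comparator has d=0.26 and the other measure d=0.39 (1.5 times) or 0.52 (2 times). With h = 1/n1+1/n2 and N = n1+n2, the fuller variance is 2h + (dA²+dB²)/(2N) − 2[rho·h + rho²·dA·dB/(2N)]. At rho 0.5, 240/240 and 1.5 times, the standard error is 0.0922, 0.13/0.0922 = 1.41, and power is 0.29.

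| rho | 1.5×, 240/240 | 1.5×, 120/120 | 2×, 240/240 | 2×, 120/120 |
|---|---|---|---|---|
| 0.3 | 0.22 | 0.14 | 0.66 | 0.39 |
| 0.5 | 0.29 | 0.17 | 0.80 | 0.51 |
| 0.8 | 0.60 | 0.35 | 0.99 | 0.87 |
| 0.9 | 0.88 | 0.60 | 1.00 | 0.99 |

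Simulation with re-estimated SDs at rho 0.4, 0.6 and 0.8 agreed with the formula to about one percentage point for the 1.5-times case, with type I error about 0.053.

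**5. Correlations.** For r=0.20 at n=600, Fisher's z gives 0.2027 × √597 = 4.95, so power is above 0.99. This part is not short of power.

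**The case against.** The plan is open about what it powers. It names the cohorts, the effect sizes and the sidedness, and nowhere says that it has 0.80 power to show one measure beats another. Only the heading suggests wider coverage. Section 7.1.2 proposes to summarize relative sensitivity, with no null hypothesis or alpha, so power for a formal test concerns a test the plan does not contain. Both the 1.5-times advantage and rho are assumptions. At rho 0.9 with all children, or with a doubled effect at rho 0.5, power for the comparison reaches 0.80 or more.

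Most of this stands, and it limits the point. A reader might infer that the 0.80 is miscalculated; it is not, for its own contrast. A reader might also infer that Aims 1 and 2 as a whole are underpowered. The documents do not support that: Objective 1.1 and the primary outcome in Section 5.3 are correlations, Objective 2.1 concerns correspondence with earlier trajectories, and the mixed models address predictive validity. The between-measure comparison is one strand of these aims.

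What does not stand is that calling the comparison a summary makes precision irrelevant. The hypotheses in Section 3.0 are comparative, and larger statistics are to be read as greater sensitivity. A conclusion drawn that way needs a measure of its uncertainty. The loss of half the sample for the dynamic score needs no assumption about rho at all.

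**Conclusion.** The concern holds in a limited form. The power of at least 0.80 is sound for a cohort difference on a single score available in all children. At the same planning effects it falls to about one half for the BPG dynamic score, and it says nothing about whether one measure discriminates cohorts better than another.

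For that comparison the documents fix neither the difference of interest nor rho, so no single power figure can be given. What can be said is that at rho 0.5 with all children, the detectable excess (0.26 SD) equals the whole planning effect for HEU vs HUU, so the better measure would need about twice the comparator's d. With the dynamic score the requirement is larger still. These figures assume that the Mullen-based d=0.26 carries over to the comparator, that the cohorts are complete, and that there is no covariate adjustment. Aim 3, also under the heading, was not assessed here.

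**What to change.** 1. In Section 7.1.2, restate the power sentence as covering a cohort difference on a single measure available in all children. Beside it, give 0.52 (120 vs 120, d=0.26) and 0.50 (60 vs 120, d=0.31) for the BPG dynamic score.
2. For between-measure comparisons, state the detectable paired difference in standardized effect at the number of children who have both measures, with rho as a declared assumption. For HEU vs HUU this is about 0.16 to 0.30 SD at 240/240 for static BPG vs gold standard (rho 0.8 to 0.3). It is about 0.23 to 0.43 SD at 120/120 for any contrast with the dynamic score, rising to 0.51 at rho 0.
3. In the analysis text for Aims 1 and 2, report a 95% confidence interval for the paired difference in standardized effect, that is, the cohort contrast of the within-child difference between standardized scores, all oriented the same way. An interval for the relative validity ratio would also serve. Claim greater sensitivity only if the interval excludes no difference; otherwise report the estimates as estimates.

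The cost is a less favourable stated power and one extra contrast on data already being collected. No children or visits are added.
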